## 2.5 Preliminary results

We have previously demonstrated good performance of LEAD ultrasound in neonates to show highly detailed brain vasculature and suppression of flash- and motion-artifact. In addition, we used this technique for deep imaging within the liver (~22 cm), which overcomes difficulties of imaging large or obese individuals with high body mass index (unpublished results, see Figure).

**Figure: Demonstration of LEAD applied to the liver of a high BMI individual.** This power Doppler-style image shows sensitivity to a wide range of vasculature deep within the liver. The smallest vessels visualized are on the order of 1 mm in diameter.

## 2.6 Study Design

This is a pilot, single group imaging study, testing a new method of therapeutic response assessment, power Doppler ultrasound, in mRCC patients treated with TKI plus ICI (arm 1) or non-ICI therapy (arm 2). A total of 30 subjects will be enrolled for a two-arm, open-label cohort. No randomization is used. Rather, subjects receiving the treatment as part of their standard of care are followed with the ultrasound studies. Since this is an exploratory pilot study and we are not formally testing a specific research hypothesis, the sample size for each arm has been chosen based on practical considerations and estimated feasibility.

### 3. PARTICIPANT SELECTION AND ENROLLMENT PROCEDURES

#### 3.1 Inclusion Criteria

The participant population consists of patients treated at Stanford Healthcare or patients referred to Stanford from outside institutions for participation in this study. Patients must meet all of the following general inclusion criteria:

- 18 years of age or older
- pathology-confirmed diagnosis of RCC
- at least one tumor lesion greater than 1 cm in diameter, amenable to ultrasound imaging
- written informed consent.

In addition, patients must meet the following specific inclusion criteria for the respective study arm:

##### Arm 1: TKI plus ICI Treatment

- planned to be treated with combination of VEGFR2 tyrosine kinase inhibitor (TKI) plus immune checkpoint inhibitor (ICI)\*

\* prior use of either class of drugs is not necessarily excluded, and patients may be included with the approval of the Protocol Director

##### Arm 2: Non-ICI Treatment

- planned to be treated with non-ICI therapy\*\*

\*\* including, but not limited to: TKI monotherapy, other kinase inhibitors (e.g., mTOR inhibitors) alone or in combination with TKIs, localized tumor therapy such as radiation, chemo- or radioembolization

Subjects may participate in the study more than once at the discretion of the Protocol Director, for example, if they receive different lines of treatment that all qualify for the study.

#### 3.2 Exclusion Criteria

Any comorbid condition\*\*\* that, in the opinion of the treating provider or the Protocol Directors, compromises the participant's ability to participate in the study.

\*\*\* Examples: any mental condition that compromises the ability to follow a consent discussion or to make informed decisions (except if represented by a Legally Authorized Representative [LAR]) or to have ultrasound exams.

#### 3.3 Informed Consent Process

No advertisements are utilized. All participants must be provided a consent form describing the study with sufficient information for participants to make an informed decision regarding their participation. Participants are consented by a member of the study personnel at Stanford Healthcare, Stanford University, or remotely. Remote consent discussions will take place via telephone or video conferencing services (e.g., Stanford instance of Zoom, EpiC video visit). The

remote consent process does not waive the requirement for written consent and the investigators must follow the Stanford Cancer Institute's SOP 'Remote Consenting for Adults' to obtain written consent. Participants or their Legally Authorized Representative (LAR) must sign the IRB-approved informed consent prior to participation in any study specific procedure. Written consent may be obtained electronically via Adobe Sign. The participant must receive a copy of the signed and dated consent document. The original signed copy of the consent document must be retained in the medical record or research file.

### **3.4 Study Timeline**

The study will reach primary completion 2 years from the time the study opens to accrual.

### **3.5 Study Completion**

The study will reach study completion 3 years from the time the study opens to accrual.

## **4. IMAGING PROCEDURE INFORMATION**

The ultrasound exams must be performed either by a licensed professional (technologist, fellow, or attending) or by a qualified member of the research staff (e.g., research scholar, fellow), if all of the following criteria (approved by the Stanford School of Medicine Department of Radiology and Stanford Healthcare) are fulfilled:

- delegated individual holds a sonography certification
- task is delegated by the Protocol Director and this is documented on the Delegation of Responsibility Log
- a California-licensed radiologist interprets the sonography (not applicable to this study, as the study does not include any formal interpretation of the ultrasound exams)
- the clinical ultrasound machine is set up with a research function to keep clinical care and research separate (not applicable to this study, as all scanners are exclusively used for research).

Performing the exam includes holding the transducer, providing patient care related to the exam in collaboration with the investigators, and documenting the encounter in the patient's Stanford Healthcare medical record. Investigators with expertise in ultrasound are allowed to be present and provide assistance with operating the instrument to the licensed professional. Assistance may include image review, instrument operation during the scan, but not providing any patient-related care or holding the transducer.

The selected lesions (see section 10.3.2) are imaged in B-mode and with power Doppler ultrasound using a portable Siemens Acuson S3000 ultrasound scanner and a 6C1 or similar transducer, in the long axis and short axis planes, if possible by localization. For LEAD ultrasound exams, the same views using a Verasonics Vantage 256 scanner with a C5-2v or similar transducer are obtained. The ultrasound exams take place during standard-of-care or research-only clinic visits at Stanford Healthcare.

Each participant has three ultrasound exams, each with both scanners: at treatment 'baseline' and 3 and 6 weeks after initiating treatment.

## 5. STUDY PROCEDURES

### 5.1 Criteria for Removal from Study

Subjects are removed from active study participation (i.e., no further ultrasound exams), if

- they are non-compliant with study procedures;
- their treatment plan changes before the first ultrasound exam such that the new treatment plan does not qualify for this study;
- they start a different treatment during the active study participation period;
- for participants in arm 1, they receive less than 4 weeks of TKI treatment during the first 12 weeks after initiating TKI plus ICI therapy (i.e. minimum 4 of 12 weeks of TKI treatment and minimum one dose of ICI required for continued study participation);
- for participants in arm 2, they receive less than 4 weeks of systemic therapy during the first 12 weeks after initiating treatment. (For localized therapies, the minimum treatment requirements are determined by the Protocol Director.)

Subjects removed from active study participation with valid written consent are followed up per study protocol, so that data acquired by study procedures up to that time point can still be used for analysis.

### 5.2 Alternatives

As an alternative to this study, the patient may elect not to participate. Patients will continue to receive standard care through their oncologist.

## 6. STUDY CALENDAR

	Pre-Study	Baseline (up to 28 days prior to initiating therapy) h	Standard-Of-Care Therapy			
			Week 3 (+/- 8 days) i	Week 6 (+/- 15 days) i	Week 12 (+/- 4 weeks) h	Before Study Completion j
Informed consent	X					
Doppler ultrasound exams a		X	X	X		
Standard-of-care imaging b	X				X	
Adverse event evaluation c				X		
Recording of age, race, ethnicity, sex, diagnosis, cancer stage, tumor histology, and drug treatment d,e				X (just once during any study timepoint)		
Documentation of lesions selected for ultrasound exam, scanners and modalities used, and imaged axis planes		X	X	X		
Quantification of tumor perfusion parameters f						X
Tumor diameter measurements g						X
Optional recording of medical history and other diagnoses, concurrent treatment and medication, additional treatment, follow-up, and survival data for future correlation studies e		X				X

a) Doppler ultrasound exams: power Doppler and LEAD ultrasound exams, performed during standard-of-care clinic visit or at research-only visit; if exam can be performed only with one of the two ultrasound scanners, only in one axis, or if one time point is missed entirely, subsequent exams may still be performed in full within their allowed time window.
 
b) Standard-of-care imaging: The baseline standard-of-care scan is generally within 6 weeks prior to initiating therapy, but may be greater than 6 weeks prior to therapy, if this is the scan that the treating physician chooses to use as reference for response evaluation. Preferably, this is a CT Chest-Abdomen-Pelvis (CAP) scan (with or without contrast), but it may also be an MRI or PET/CT or a combination of MRI and CT. At the discretion of the treating oncologist, the standard-of-care scan at week 12 may be performed outside of the +/- 4-week window.
 
c) Adverse event (AE) evaluation: Only AEs that are attributed to the study procedures are recorded and reported. During study procedures, study coordinator reminds patient to contact the clinical care team, if they experience any symptoms during the exam or afterwards. If the participant expresses to the coordinator that they have experienced symptoms during or after the exam, the coordinator will alert the clinical care team on the same day to contact the patient for AE evaluation and management. During baseline through week 12, patient will continue with standard-of-care provider visits at or outside of Stanford (generally, every 2-6 weeks, at the discretion of the treating clinical care team) including adverse event management. At week 12, a retrospective chart review will document any undisclosed study-related late adverse events and assure there are no ongoing study-related adverse events. If there is no adequate information in the medical record at week 12, patient will be contacted if needed to complete this documentation. Therefore, at minimum, there is one documented AE evaluation at week 12.
 
d) to be recorded once between baseline and study completion
 
e) may be obtained until study completion, even after a participant's death; patients or their outside medical providers may be contacted as needed to obtain the clinico-demographic data, if not available in the Stanford medical record.
 
f) to be quantified and recorded for all ultrasound exams from this study
 
g) RECIST measurements to be recorded for all imaging studies used for response evaluation (CT, MRI or PET/CT as described in footnote (b)). Performed at minimum at baseline and 12 weeks. RECIST measurements will also be recorded for other subsequent standard-of-care studies that the treating MD obtains at any interval to evaluate treatment response (until 12 months after initiating treatment or until end of the treatment that is being studied, whichever occurs first)
 
h) For combination treatments, initiation of therapy is typically defined by the day of starting treatment with the second drug, however another day (such as the start of treatment with the first drug) may be defined as start of treatment at the discretion of the Protocol Director; date considered start of treatment will be documented in the research procedure note in the electronic medical record.
 
i) 10 days is the minimum time period between week-3 and week-6 power Doppler ultrasound exams; similarly, 10 days is the minimum time period between week-3 and week-6 LEAD ultrasound exams; it is not required that power Doppler and LEAD ultrasound exams are performed on the same date.
 
j) Before end of study (3 years from date of study opening)
						

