## 9.2 Secondary Outcome Measures

Secondary endpoints are:

- 1) **initial relative change in tumor burden** (continuous): defined as relative change (i.e., difference between time points divided by value at time point 1, expressed as percentage) in the sum of all tumor diameters between treatment 'baseline' and first on-treatment response evaluation 8-16 weeks after start of treatment, using RECIST v1.1 for tumor diameter measurements, expressed as mean +/- standard deviation and median with interquartile range
- 2) **initial lesion response** (continuous): defined as the relative change in tumor diameter of a single lesion between treatment 'baseline' and first on-treatment response evaluation 8-16 weeks after start of treatment, using RECIST v1.1 for tumor diameter measurements, expressed as mean +/- standard deviation and median with interquartile range.
- 3) **12-month progression-free survival (PFS)** (yes/no): defined as not having experienced any PD per RECIST v1.1 within the first 12 months after initiating treatment (day 1 will be treatment start date), as a number and proportion without dispersion.

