### **9.2.1 Measurement Methods**

Tumor diameter measurements: same as for primary endpoint

Progression-free survival: determined by medical record review and contacting participants or their outside medical providers as needed.

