### **9.2.2 Measurement Time Points**

Initial response evaluation is performed by radiographic imaging at the same timepoints as for the primary endpoint. For repeat response evaluations on treatment, standard-of-care restaging imaging studies will be used. These, as well as determination of 12-month PFS, require follow-up at 12 months after initiation of treatment.

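### RECIST recording may stop when the studied treatment ends, but 12-month PFS is defined by RECIST progression over a full 12 months, so detection of progression depends on time on treatment

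*Protocol*

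**What the plan says.** Three parts of the protocol bear on how long progression is measured.

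- **Section 6, footnote g** (attached to the tumor diameter row of the calendar) requires RECIST measurements at baseline and week 12. For later scans, "RECIST measurements will also be recorded for other subsequent standard-of-care studies that the treating MD obtains at any interval to evaluate treatment response", but only "until 12 months after initiating treatment or until end of the treatment that is being studied, whichever occurs first".
- **Section 9.2, item 3** makes 12-month PFS a yes/no endpoint, "defined as not having experienced any PD per RECIST v1.1 within the first 12 months after initiating treatment", reported as a number and proportion. Nothing in it refers to time on treatment, and it has no category for patients who cannot be evaluated.
- **Section 9.2.2** says that repeat evaluations and "determination of 12-month PFS, require follow-up at 12 months after initiation of treatment".

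Section 9.2.1 adds a separate route to PFS status: it is "determined by medical record review and contacting participants or their outside medical providers as needed". Section 10.4.2 plans a Kaplan-Meier estimate of PFS and also a Pearson or Spearman correlation of perfusion change with PFS to 12 months, in each arm.

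**The concern.** The endpoint is defined by a measurement that the calendar no longer requires once treatment ends. Take a patient who stops for toxicity at month 4 and progresses at month 8. The endpoint window is still open at month 8, but footnote g does not call for the scan to be read by RECIST. Because a yes is defined by the absence of PD, a gap in measurement and a true absence of progression can look the same in the data.

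The period over which PD can be found then varies with treatment duration. Two patients with the same disease course could be classified differently because one stayed on drug longer. If perfusion change is related to how long patients stay on treatment, the planned correlation with 12-month PFS would partly reflect ascertainment. In arms of 20 and up to 10 patients, one or two misclassified patients can visibly move a proportion or a correlation.

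**Working it through.** **Comparison of the passages.** The protocol states no PFS rate, discontinuation rate or event count, so there is no figure of its own to reproduce. The main check is of consistency.

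| Question | Footnote g | Sections 9.2 and 9.2.2 |
|---|---|---|
| When does the window end? | Month 12 or end of studied treatment, the earlier | Month 12 |
| Does it depend on staying on treatment? | Yes | No |
| What establishes PD? | RECIST measurements, while recorded | PD per RECIST v1.1 |

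For a patient still on treatment at month 12 the two agree. For a patient who stops earlier without PD they do not. Section 9.2.2 shows the same restriction in its own imaging sentence: "For repeat response evaluations on treatment, standard-of-care restaging imaging studies will be used".

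**Where the gap is widest.** Arm 2 admits "localized tumor therapy such as radiation, chemo- or radioembolization". If such treatment is completed before week 12, footnote g requires nothing after the week-12 scan. Week 12 is about month 3, so 12 − 3 = about 9 months of the window have no required RECIST measurement.

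**Whether other provisions close it.**
- Section 9.2.1 has no stop at the end of treatment and can bring in progression reported by outside providers. It does not say how a report becomes PD per RECIST when no measurements are recorded.
- Section 5.1 says "Subjects removed from active study participation with valid written consent are followed up per study protocol". This keeps such patients in follow-up, but the RECIST part of that follow-up is the one in footnote g.
- The calendar row for later follow-up and survival data is optional and is meant for future correlation studies.
- Kaplan-Meier can censor. The number and proportion in section 9.2 and the correlation coefficients in section 10.4.2 cannot.

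**Illustrative size, on assumptions not found in the protocol.** Suppose PD after stopping is never captured and is read as no PD. Let S be 12-month PFS if the on-treatment PD hazard applied throughout, d the probability of stopping by month 12 if PD did not intervene, and k the ratio of the PD hazard after stopping to that on treatment. With constant hazards:

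- λ = −ln(S)/12 and θ = −ln(1 − d)/12
- PD seen on treatment = λ/(λ + θ) × [1 − exp(−12(λ + θ))]
- Proportion scored progression-free = 1 − PD seen on treatment
- Overstatement = PD after stopping but before month 12

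Example, S = 0.60, d = 0.20, k = 1: λ = 0.0426, θ = 0.0186, and exp(−12(λ + θ)) = 0.60 × 0.80 = 0.48. PD seen = 0.696 × 0.52 = 0.362, so 63.8% are scored progression-free against a true 60.0%. The overstatement is 3.8 points, or 0.76 of 20 patients.

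| S | d | k | True | Scored | Excess of 20 |
|---|---|---|---|---|---|
| 0.70 | 0.10 | 1 | 70.0% | 71.4% | 0.29 |
| 0.60 | 0.20 | 1 | 60.0% | 63.8% | 0.76 |
| 0.60 | 0.20 | 1.5 | 58.5% | 63.8% | 1.05 |
| 0.50 | 0.30 | 1.5 | 47.5% | 57.1% | 1.91 |

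Over S = 0.50 to 0.70, d = 0.10 to 0.30 and k = 1 to 1.5, the overstatement runs from 1.4 to 9.5 percentage points (0.3 to 1.9 of 20). If all later PD is captured, it is zero.

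**The case against.** The strongest reply is that footnote g governs tumor diameter measurements, while PFS has its own method in section 9.2.1 that does not stop with treatment. Section 9.2 speaks of PD experienced, not PD recorded, so a patient known from the chart to have progressed at month 8 is not progression-free. Footnote g sets a minimum and does not forbid reading a later scan. Kaplan-Meier is already planned, and censoring and evaluability rules are commonly left to a statistical analysis plan, which is not at hand. Finally, restricting RECIST reading to the studied treatment is a defensible choice for a marker of response to that treatment.

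Much of this stands. A reader might infer that patients who stop early are scored progression-free by default; no passage says so, and record review may catch some of their progressions. A reader might also infer that the rule fails throughout arm 2. That arm includes TKI monotherapy and other kinase inhibitors, which may continue, so the 9-month gap applies only to localized therapies completed before week 12, an unknown share of up to 10 patients. Nor does the protocol support saying that early stoppers are the patients with poorer outcomes. The absence of detailed censoring rules is not part of this point.

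What does not fall away is the contradiction itself. The protocol states a rule that ends the measurements on which its endpoint is defined, and record review is not RECIST assessment. If on-treatment progression was intended, sections 9.2 and 9.2.2 describe a different endpoint and need to say so.

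**Conclusion.** The point holds as an inconsistency between footnote g and sections 9.2 and 9.2.2. It leaves PD per RECIST without required measurements for part of the 12-month window in patients whose treatment ends early, and the yes/no definition permits counting them as progression-free. The likely direction is an overstated 12-month PFS proportion; the effect on the correlation with perfusion change cannot be signed from the protocol.

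The size is unknown. The figure of about 0.3 to 2 of 20 arm 1 patients rests on assumed stopping and progression rates, constant hazards, and no capture of progression after treatment. Successful record review would reduce it.

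The consequence is limited. Section 1.2 lists the PFS correlation among additional exploratory objectives, section 9.1.2 says the primary endpoint needs no further follow-up, and the criterion for a follow-up study in section 10.7 is an AUC. A reader should not infer that the primary analysis or that criterion is affected. The change is worth making, but the study does not turn on it.

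**What to change.** Reconcile footnote g with sections 9.2 to 9.2.2. The simplest way is to replace the stopping clause in footnote g so that RECIST measurements are recorded from all available standard-of-care response scans until PD, death or 12 months after initiating treatment, whether or not the studied treatment has ended. The phrase limiting repeat evaluations to those on treatment in section 9.2.2 should be aligned.

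In section 9.2, item 3, add that patients without PD assessment to about month 12 and without earlier PD are not counted as progression-free in the yes/no proportion. They can be reported as not evaluable, or the 12-month figure can be taken from the Kaplan-Meier estimate already planned.

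The cost is a short amendment and additional reading of scans done anyway. No visits, procedures or treatment decisions change. The calendar places tumor diameter measurements before study completion, so the readings can be made retrospectively. The downsides are retrieving some scans from outside providers, whom section 9.2.1 already expects to contact, and possibly a less favourable PFS proportion.

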
## 7. ADVERSE EVENTS AND REPORTING PROCEDURES

### 7.1 Potential Adverse Events

There are no known risks from ultrasound as a diagnostic tool in its 60 years of use. The Verasonics system used for LEAD ultrasound exams operates the same way as a regular ultrasound system, except the investigators are performing the acoustic output measurements instead of the manufacturer. The system has also been cleared by Clinical Engineering. Therefore, the risks are no different than a clinical ultrasound scanner such as the FDA-approved Siemens system used for the conventional power Doppler ultrasound exams. We have also previously used the Verasonics system in several IRB-approved protocols in studies involving imaging of adult liver, adult heart, adult thyroid, and neonatal brain. There have been no adverse events in any of these studies or subjects/patients.

Possible adverse events from the procedure include discomfort or tenderness in some cases from slightly pressing the transducer against the tumor site. However, protocol directors are available in the event of an unforeseen adverse event or the need for medical intervention.

